**Hiring and Training Outcome Assessors and Intervention Facilitators.** Our research team will initially come from our existing team who worked on the previous study and/or who have previously conduct adolescent focused HIV/STI prevention research and interventions. Then we hire additional team members if needed based on experience relevant to the study. Our team will be split into an outcome assessment team (based at DTHF) for Aim 1 and an intervention team (based at Department of Psychiatry at UCT). We will draw from both for Aim 3. Our investigative team will train our outcome assessment team in data systems, procedures, protocols, and forms using mock training as well as in-field practice to ensure quality data collection and preparation for successful tracking and tracing. Outcome assessors will be *blinded*. We will also train our intervention and fidelity team in protocols, procedures, and forms including randomization and delivery of the *Our Family Our Future* intervention. Training will involve 4 modules. Module 1 includes: 1) introductions and ice-breaking exercises, 2) project overview and training objectives, 3) education regarding depression, HIV, parenting, family communication, gender roles and social norms particularly in regards to sexual relationships, and sexual relationship negotiations. Module 2 focuses on intervention facilitation skills: 1) public speaking and 2) communication of sensitive topics. Module 3 involves training in use of the manualized intervention protocol including: 1) demonstrations of intervention modules, 2) education on core intervention elements, and 3) role-play. Module 4 involves: 1) testing facilitation skills in short mock scenarios, 2) feedback from the PIs. We incorporate challenges that may arise during intervention implementation including delivery of intervention content and inter-personal interactions to assess facilitators' mastery of core. We rank performance using fidelity forms. If an interventionist is not deemed qualified, additional training will be provided until competent. Interventionists deemed unqualified will be replaced.

## 2. Study design

**Summary of scientific design.** We test the efficacy of *Our Family Our Future* in a 2-arm, single blinded RCT with 6- and 12-month follow-ups. Participants include a sample of N=880 adolescents 14-16 years (and 880 parents) who will be randomized based on permuted blocked randomization (balancing by gender) to an intervention arm (n=440 adolescents and their parents testing *Our Family Our Future*) or a control arm (n=440 adolescents and their parents) of usual care. Study design carefully adheres to elements outlined in the Consolidated Standards of Reporting Trials (CONSORT) Statement. This pilot study adheres to a single blind, randomized pilot trial design with the end goal of informing a full-powered RCT corresponding to a Phase III

---

 The 12-month follow-up with parents and teens may occur up to 24 months afterwards in order to retain as many teen/parent dyads as possible in the longitudinal analysis.

clinical trial. Outcomes will be assessed at baseline, 6 months, and 12 months after the last intervention session. Due to the COVID-19 crisis (March, 2020) we will attempt to first abide by the scheduled 6- and 12-month outcome timepoints for all self-reported and behavioral data with biological data (HIV and STIs) captured when movement restrictions are lifted and/or when physical contact is acceptably safe. If this does not work, we will shift to collecting all 6- and 12-month timepoints for all data to when movement restrictions are lifted and/or physical contact is acceptably safe. The count-down clock for the 6 months and 12 months outcome evaluations will occur after the last intervention session has occurred. Feasibility data and process data on possible mechanisms of change will be collected at eligibility, enrollment, during the intervention sessions, and during baseline and follow-up assessments.

**Study questions.** The primary study questions are:

Question 1: Is this intervention efficacious? That is, is there evidence of hypothesized effects of the intervention, that the intervention will reduce or maintain symptoms that fall below the clinically significant range for depression and reduce or delay actual or intended sexual risk behavior in adolescents?

Question 2: What mediates and moderates the effect of the intervention on the main outcomes?

Question 3: What are the barriers and facilitators of intervention implementation?

**Intervention summary.** *Our Family Our Future* is a 'selective' prevention program, designed to address HIV/STI acquisition, sexual risk behavior, and depression among adolescents (ages 14-16) in communities with high HIV prevalence and from families where adolescents exhibit mild, potentially troublesome, depressive symptoms but do not reach the threshold for further screening for a significant clinical depressive disorder. The preventive intervention is comprised of the integration and adaptation of two existing empirically supported models that were ranked "best-evidence" models for preventing HIV (Keepin' It Real) and depression (Family Talk). The two interventions will be integrated into one combined intervention, given the syndemic relationship between outcomes with depression elevating risk for adolescent sexual risk and because the original interventions use similar techniques to improve mood and sexual safety and thus, are appropriate for integration and delivery simultaneously in one adapted intervention.

This intervention involves parent-child dyads who receive the intervention in a community setting, in a facilitated group format. Due to the COVID-19 crisis, we will use an alternative format as an option of individual family sessions with facilitators, delivered by telephone. The intervention is comprised of 3-hour sessions, held weekly for 3 consecutive weeks with an individual family meetings in the third or fourth week depending on family desires. The intervention also includes take-home activities to deepen behavioral engagement with the week's received session and to "prime the pump" for the upcoming week's session. The final intervention covers the following topics in combined adolescent-parent sessions using role play, group activities, discussion and debate, and facilitation: 1) family needs and values; 2) community strengths and challenges; 3) communication skills; 4) talking about sensitive topics – HIV, STIs, sex, puberty, mental health, and discipline; 5) HIV and STI transmission, prevention, and living with HIV; 6) healthy individual and family coping with mental distress, adolescent sexual health, and other challenges; and 7) family goals and strategies for healthy interactions and problem-solving. There are also separate adolescent and parent sessions. For adolescents, topics include: 1) peer influences; 2) healthy relationships and gender roles and interpersonal violence; 3) sexual decision making and communication; 4) condom use and contraception; and 5) consequences of sexual decisions. For parents, these include: 1) adolescent development and reproductive health; 2) healthy

relationships and gender roles; 3) psychoeducation on depression; 4) communicating about sexual and mental health; and 5) condom use and contraception.

We outline signature elements of *Our Family Our Future*:

- **Theory driven and developmentally appropriate adolescent HIV/STI prevention:** *Our Family Our Future*'s adolescent HIV/STI prevention components are taken from the original HIV intervention – *Keepin' It Real* – which had some of the largest effect sizes for condom use ( $d=0.89-1.68$ ) in Johnson's global meta-analyses of 67 adolescent HIV prevention trials. *Keepin' It Real* was ranked "best-evidence" by the Centers for Disease Control and Prevention. The theoretical premise of *Our Family Our Future* (and *Keepin' It Real*) is Information-Motivation-Behavioral (IMB) theory and informed by adolescent development theory on the salience of family involvement in prevention. The change strategy of the HIV/STI prevention and risk reduction components include: (1) increasing HIV/STI knowledge around protective behaviors (i.e., information), (2) encouraging adolescents to implement protective behaviors through for example, facilitating positive family involvement in addressing adolescent sexual and reproductive health challenges, linking protective HIV/STI behaviors to future goals, and formation of positive peer relationships that impact attitudes towards HIV risk(i.e., motivation), (3) building self-efficacy for prevention behaviors including condom use, condom negotiation, and healthy sexual relationships (i.e., behavior). The intervention includes adolescents regardless of HIV status given careful community buy-in that indicated it was unacceptable to further stigmatize children based on HIV positive status by excluding them, and since they are also in need of prevention.
- **Integration of rigorous global evidence on adolescent HIV/STI prevention:** Our adolescent HIV/STI prevention approach was further strengthened with integration of rigorous HIV/STI prevention evidence systematic reviews and/or meta-analyses. The first meta-analysis evaluated effective HIV interventions for South African youth aged 9-26 years ( $k = 11$ ;  $N = 22,788$ ) and showed interventions were efficacious in delaying sexual intercourse, increasing condom use, reducing the number of sexual partners relative to those in a control condition, and lowering incidence of HSV-2. Based on this, we will include: delivery by facilitators who are not professionals (e.g., not nurses); delivery over fewer sessions (e.g. length was not important); content covering social norms and gender inequalities; and incorporation of intensive behavioral skills training. We further examined whether brief interventions for HIV prevention have a clinically significant effect in a second meta-analysis evaluating effectiveness of single-session behavioral interventions to prevent STIs ( $k = 20$ ;  $N = 52,465$ ); this showed intervention participants relative to controls had significantly lower risks for STIs. Based on this, we focused on a brief but behaviorally intensive intervention since brief preventive (individual, group-based, computer delivered) interventions can have clinical salience. The third meta-analysis evaluated effectiveness of HIV interventions for adolescents 11-19 years globally ( $k = 67$ ;  $N = 51,240$ ), and showed intervention participants relative to controls had significant reductions in incident STIs, frequency of sex, number of partners, and significant increases in abstinence or delay of intercourse, condom use, safer sex communication skills, and acquisition of condoms. Based on this, we enhanced the following components: motivational for behavior change and condom skills training but no emphasis on abstinence given abstinence focused interventions were ineffective. The fourth global meta-analysis was on the efficacy of behavioral interventions to increase condom use and reduce STIs ( $k = 67$ ;  $N = 40,665$ ) and showed intervention effects of increased condom use, fewer incidents of STIs, and lowered cases of HIV. Based on this, we will include: for motivation, focusing on distal motivation components (i.e., future orientation for adolescents); and content with behavioral skills training (i.e., condom skills and interpersonal skills).
- **Theory driven, best-evidence adolescent depression prevention:** *Our Family Our Future*'s adolescent depression prevention components are taken from the original depression

intervention – *Family Talk* – which showed efficacy lowering depressive symptoms ( $d=0.32$ ), has been adapted for diverse linguistic, cultural, and socioeconomic populations, and was ranked best-evidence by the Substance Abuse and Mental Health Services Administration. This intervention is informed by cognitive behavioral theory and resilience theory, emphasizing individual- and family strengths, and facilitating resilience-boosting factors such as education, coping, and healthy family interactions. In addition, the intervention is future-oriented to help families develop strategies to cope with forthcoming challenges. The intervention focuses on intervening with families experiencing some distress but not with depression (families with depression need treatment rather than prevention). The change strategy of the depression prevention components include: 1) psychoeducation including specific education of family dynamics of depression; 2) empowering parents to communicate about mental health; 3) cognitive-behavioral strategies including development of recognizing and changing negative thoughts and behaviors and practicing positive coping strategies; 4) supporting healthy family interactions; and 5) creating family strategies and a common narrative around the family experience of mental health.

- **Linkages between HIV/STI and depression:** The intervention increases understanding of linkages between HIV and depression. This includes for example, how negative affect can alter perceptions of risky situations and partners, and how maladaptive coping with emotional dysregulation such as substance use can negatively impact implementation of protective behaviors. This also includes for example how parental depressive symptoms can affect communication and healthy family interactions. The intervention builds self and family efficacy in behavioral strategies to address these interactive risks between HIV/STI risk and depression.
- **Building prevention facilitating family environments:** The intervention incorporates insights from adolescent development theory to build facilitating family environments that can be leveraged to enhance adolescent prevention outcomes. The intervention focuses on family elements critical for both prevention of adolescent depression and HIV/STIs including communication and functioning. The intervention empowers families by using a facilitated process to identify a family's unique strengths and to build on these for maximum intervention impact. The intervention encourages families to map their family's unique goals in their own tailored journey through the intervention and to create family strategies to overcome their specific challenges.
- **Integration of appropriate strategies and modalities for behavior change:** *Our Family Our Future* has been adapted to included visual content to encourage active communication and to overcome low-literacy; and to boost interaction through fun games and debate. The intensity of the intervention is extended through take home activities to reinforce behavior. The intervention is delivered in local language (ixiXhosa) and includes culturally specific concepts of resilience and context specific strategies to build family resilience based on careful formative qualitative work conducted during the K01. The format, delivery, and modality of preventive interventions has been carefully considered to ensure future scalability and sustainability in an overburdened health system with 0.28 psychiatrists, 0.45 other medical doctors, 7.45 nurses, 0.32 psychologists, 0.4 social workers, per 100,000 population in South Africa. Our partnership with Desmond Tutu HIV Foundation (M-PI [name] and co-I [name]) – was chosen strategically; they are a large-scale organization capable of bringing *Our Family Our Future* to scale for implementation if found to be efficacious.

**Blinding.** This will be a single blind study. Intervention participants will not be blinded to the condition they are in (the intervention group will receive the intervention first, with the control group given usual care (*i.e.*, health resources). Study staff (e.g. intervention team) will not be blinded to the condition. Study staff (e.g., assessment team) who assess outcomes after the experimental intervention has been delivered will be blinded to the condition participants have been assigned to. Blinding will be broken for data analysis. To reduce the risk of contamination,

or that blinding will be broken by participants communicating to each other, we will request that participants in the intervention keep all activities and discussions to themselves. We will also assess whether blinding was successful by checking for contamination at the outcome assessments that occurs at 6- and 12-months. There is no chance that dyads in the control group would participate mistakenly in the intervention so we assess for contamination in terms of sharing of intervention materials between the intervention and control group. Dyads assigned to the control group will be screened for contamination. We will adjust for any contamination effects in analyses.

**Design considerations – parent involvement and control condition.** We carefully considered the choice of one parent participating. For the purposes of this efficacy trial, a consistent parent attending the intervention ensures that we can deliver an appropriate dose of the intervention. For example, consistent participation of one parent enables that parent to better learn the full suite of intervention skills (such as modeling of positive family relationships and communication) needed to support prevention of adolescent HIV/STI and depression. Furthermore, involvement of one consistent parent protects the integrity of the efficacy trial, allowing us to clearly identify what parent should be involved in baseline and follow-up surveys. We additionally clarify that intervention materials have been designed in such a way that they can be used by more than one parent. Given the design of materials where involvement of multiple family members is possible, we are prepared to extend the intervention model to include multiple parents and adolescents in the follow-up of this efficacy trial (if there is evidence of efficacy), which will be an implementation/effectiveness trial.

We chose the control after extensive thought and discussion during trial design. We decided on a control condition of usual care (a packet of existing available brochures on HIV, STIs, mental health including places to access care) based on previous data, ethical and policy considerations, and tradeoffs between cost and science. First, in regards to previous data, the intervention being tested in this efficacy trial (*Our Family Our Future*) is an integration and adaptation of two existing “best-evidence” interventions for HIV/STI and depression prevention. The “best-evidence” ranking for the original HIV and depression preventive interventions used as the basis for *Our Family Our Future* are assigned by CDC and SAMHSA respectively after interventions have shown efficacy in multiple settings and populations. The RCTs of the original interventions were tested using various controls; importantly previous RCTs included time and attention matched controls but the original intervention showed superior efficacy. Second, we consider the ethical imperative to investigate efficacy in a manner that is salient and appropriate for the low-resource environment and policy context. There are no existing time and attention matched controls in the research setting we are working in. If we create a time and attention matched control for this trial, policy-makers will not be able to determine whether *Our Family Our Future* is superior to usual care widely available in South Africa; instead, policy makers will only be able to determine whether *Our Family Our Future* is superior to an intervention that does not normally exist in the South African context. Third, we examined what choosing a time and attention matched control would mean for the balance between cost and science. When we examined budget, adding a time and attention matched control – which would need to be newly created in this setting – would result in us shifting significant trial resources. Budget re-allocation adversely affected sample size to a point where power would be compromised. Ultimately, as we look beyond this efficacy trial to an implementation/effectiveness trial, we want to adhere to a design that is most appropriate for the complex ethical, policy, and cost versus science tradeoffs in South Africa. The usual care control condition would allow us to achieve scientific answers with the most

policy relevance, and strike a balance between costs while protecting the integrity of our main scientific goal, to have enough power to thoroughly examine the main outcomes.

**Sample Size and Power Considerations.** We use data from our preliminary pilot study and other relevant secondary sources to formulate a realistic range of necessary assumptions for sample size and power considerations for primary outcomes. As shown in Table 1 we estimate that a total sample size of 880 adolescents, or 440 adolescents per arm, will be required to adequately power our study.

[figure not shown]

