
team. However, assignment will be concealed from study staff who are part of the outcomes assessment team (single-blind) so as not to affect assessment of hypothesized effects of the intervention.

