the COVID-19 crisis, we will make two additional changes. First, regarding the time points, we will try to collect all non-biological data at the 6- and 12-month windows as planned, and then collect the biological HIV and STI outcomes when movement restrictions and/or contact precautions regarding COVID-19 transfer can be reasonably lifted. If this approach results in large amounts of missing data, we will then attempt to collect all data (biological and non-biological data) when movement restrictions and/or contact precautions regarding COVID-19 transfer can be reasonably lifted. Second, during the COVID-19 crisis, we will attempt to collect all data within a 2-8 week window, but will attempt to gather data outside of these countdown windows to limit missing data. In order to increase the reliability of measurements, for data on hypothesized effects, we choose measures informed by preliminary studies, mentor's research in South Africa, and original Family Talk and Keepin' It Real studies to be culturally and contextually appropriate. Measures have been translated previously in South Africa. We also increase reliability by focusing on measures with strong psychometric properties, and when possible with piloting and pre-testing in South Africa. In addition, we increase reliability by programming to decrease human error (e.g., logic scenarios for questions within a skip pattern). Furthermore, for sensitive questions, we administer questions via private earphones plugged into mobile data collection devices using *Audio Computer-Assisted Self-Interview Software* (A-CASI). This method has been shown to diminish social reporting bias. We will not be able to implement A-CASI if we move to remote telephone collection due to the COVID-19 crisis.

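### The contamination check named as the assessment of blinding does not measure assessor blinding, and could disclose the arm if put to control dyads alone

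*Combined protocol and SAP*

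**What the plan says.** Section 2 (Study design), Blinding paragraph, describes a single-blind trial. Participants and the intervention team know the assignment. The blinded staff are those "who assess outcomes after the experimental intervention has been delivered will be blinded to the condition participants have been assigned to". Section 3 (Recruitment and Enrollment) repeats this: because randomization takes place in a group, participants and the intervention and fidelity teams know the result, but "assignment will be concealed from study staff who are part of the outcomes assessment team".

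The Blinding paragraph then sets out how blinding will be evaluated: "We will also assess whether blinding was successful by checking for contamination at the outcome assessments that occurs at 6- and 12-months". It explains that control dyads could not end up in the intervention by mistake, and so "we assess for contamination in terms of sharing of intervention materials between the intervention and control group". The next sentence names who is checked: "Dyads assigned to the control group will be screened for contamination". Intervention dyads are not mentioned. The paragraph ends by promising that the analyses will adjust for contamination.

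Section 4, Assessment Procedures, has the assessment team guide the collection of self-reported data at the household or by phone. A-CASI is planned for sensitive questions, with this limit: "We will not be able to implement A-CASI if we move to remote telephone collection". The same section makes phone the default mode during the COVID-19 period. Section D.2 (Protection against Possible Risks) says that all non-biological data collection has been moved to phone.

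**The concern.** There are two separate problems.

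First, the plan names a procedure as its assessment of blinding that does not observe the blinded people. A low contamination rate could then be read as evidence that assessors were blind, although nothing was recorded about what they knew. A high rate could be read as failed blinding when assessors knew nothing.

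Second, the screen is described for one arm and takes place at visits run by the team that is meant to be blind. If items appear only for control dyads, whoever administers them, or sees the device branch to them, can work out the assignment.

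At stake is the credibility of blinded assessment for the self-reported outcomes. Participants know their arm and controls receive only a packet of brochures, so assessor blinding is one of the main safeguards for the CES-DC and the sexual-behaviour measures.

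**Working it through.** The plan states no figure on this point, so the check sets its statements side by side.

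**Inputs**
- Blinded party: the outcome assessment team only (the paragraph on hiring and training of outcome assessors; Section 2, Blinding; Section 3).
- What the blinding check measures: sharing of intervention materials between arms (Section 2, Blinding).
- Who is named for it: control dyads (same paragraph).
- When: the 6- and 12-month outcome assessments (same paragraph).
- Who guides those assessments: the assessment team (Section 4, Assessment Procedures).
- Any record of an assessor's guess, an unblinding event or a blinding index: none found.
- Who asks the contamination items, where they fall in the interview, and whether they are self-completed: not stated.

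**Step 1. Does the check measure blinding?** Since only assessors are blinded, a test of blinding must capture what assessors know or guess. All four combinations of the two conditions are possible:

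| | Assessor blind | Assessor knows the arm |
|---|---|---|
| Materials shared | A control family borrows a handout and the assessor never hears of it | The family mentions it in the interview |
| Nothing shared | The intended state | An intervention family mentions its group sessions |

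The check separates the rows. Blinding is the difference between the columns. The check therefore cannot assess blinding, however the questionnaire is built.

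**Step 2. Can the check reveal the arm?** Suppose the items go to control dyads alone and the assessment team administers them. Presence of the items then marks a control dyad and absence marks an intervention dyad. Timing decides which data are exposed:
- Items before the outcome measures: the self-reports of that visit are exposed.
- Items after them: the 6-month self-reports are safe from this route, and the 12-month ones are exposed only if the arm is remembered or recorded.

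A-CASI could keep the items from the assessor in person, but it is planned for sensitive questions and nothing says that these items are included. By phone it is not available.

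**Step 3. Which outcomes?** Assessor-guided self-reports are exposed. Laboratory HIV and chlamydia/gonorrhoea results are much less so.

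**Step 4. The promised adjustment.** The Aim 1 analysis plan in Section 6 contains no contamination term or method. A variable collected in one arm only cannot enter a between-arm model as an ordinary covariate.

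**Illustration only.** With 440 × 0.85 = 374 per arm, the standardized difference detectable with 80% power is (1.96 + 0.842) × √(2/374) = 0.205 SD. If knowledge of the arm shifted the arm difference by s SD, the two-sided type I error would be P(|Z + s√187| > 1.96), where 187 = 374/2. That is about 10% for s = 0.05 and about 28% for s = 0.10. Both shifts are assumptions without a source in the document. They show sensitivity, not actual bias, and the weight of this point does not rest on them.

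**The case against.** The strongest objection is that the disclosure argument relies on forms that the reader cannot see. The protocol does not say that control dyads alone are asked, and it does not say who asks. The questionnaires are in an appendix that is not part of the document, so identical items for every dyad cannot be excluded. The protocol also keeps randomization and tracking in FileMaker and survey collection in SurveyToGo, and it describes no transfer of the assignment to the survey device. All of this stands, and it limits the second part to a conditional risk.

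It is also fair to say that screening controls is sensible for contamination itself, because intervention families already hold the materials. The paragraph also treats talk between participants as a way for blinding to fail. But participants know their arm, so such talk matters for blinding only if it reaches an assessor, and the screen does not record that.

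A reader might infer more than the text supports:
- That assessors will certainly be unblinded. This depends on who is asked, by whom and when, and none of these is stated.
- That assessor blinding is the only protection for self-reports. A-CASI for sensitive items in person, programmed skip logic and field monitoring also help.
- That the plan declares blinding successful in advance. It says only that success will be assessed.
- That the type I error is known to be inflated. The shifts used above are assumed.

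None of this affects the first part: a contamination check does not measure assessor blinding, and the plan contains nothing that does.

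**Conclusion.** The concern holds in two parts of different strength. That the planned check does not assess assessor blinding follows directly from the text and needs no assumption. That it could reveal the arm is a risk, resting on two inferences: that the items go to control dyads alone, which is the natural reading of a sentence naming only them, and that the assessment team administers them, which follows from reading Sections 2 and 4 together. If both are true, the CES-DC and sexual-behaviour self-reports are exposed, chiefly in phone collection, and laboratory results much less. The amount of bias cannot be derived from the documents. The change is worth making because it is cheap and because, as written, the trial would have no valid evidence on whether its assessors stayed blind. If the items already go to both arms after the outcome measures, one sentence saying so largely settles the second part. The first part would remain.

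**What to change.** 1. In Section 2, Blinding, keep the contamination check for contamination only and stop presenting it as the assessment of blinding.
2. Put identical contamination items to both arms at 6 and 12 months, after all outcome measures, self-completed where possible. State who administers them.
3. Where feasible, do not show the answers to the assessor of a later visit. By phone, spoken answers can themselves reveal the arm, so another caller for these items, or a different assessor at 12 months, would serve the same purpose.
4. At each visit, before the contamination items are opened, record the assessor's guess of the arm and any unblinding event. Report blinding from these records.
5. In Section 6, say how contamination will enter the analysis, now that it is measured in both arms.

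The cost is a short survey amendment and slightly more interview time in the intervention arm. A separate caller or assessor, if used, adds some staff scheduling. An assessor's guess can also reflect perceived benefit, so it should be reported descriptively and not treated as a formal test of failed blinding.
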